4.6. Vital Signs

The vital signs parameters up to EOT + 3 days that will be analyzed are heart rate and blood pressure (systolic and diastolic). Position and location will only be listed.

Values and change from baseline over time will be summarized by parameter and time point, age cohort and be presented in figures as well.

All individual vital signs data will be listed.

Body Weight and Height

Height (m) (measured at Screening and Week 16) and weight (kg) data will be used in calculating the BMI.

BMI (kg/m²) will be calculated at each of these time-points. Before Week 16, BMI is calculated by using height from screening, and at Week 16 will be calculated by using height collected at

Week 16. After Week 16, BMI will be calculated from the height and weight collected at each visit.

Values and changes from baseline over time for weight, height and BMI will be summarized by age cohort and body weight group.

All individual height, weight and BMI data will be listed, and the growth curves will be presented for height, weight, and BMI as well.

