### 3.1.1 Study periods

The study consists of the following consecutive periods:

**Screening period:** Lasts up to 42 days; starts with the signature of the informed consent form (ICF) and ends with the administration of the first study treatment dose.

**Treatment period:** Starts from the first dose of study treatment at Baseline/Enrollment visit and ends on the day of the last dose of selexipag (EOT). This includes:

- **Up-titration period:**

From the first dose of study treatment until the participant reaches their iMTD. This period is estimated to last up to 12 weeks.

Details of up-titration are described in Section [5.1.4](#).

- **Maintenance period:**

**After Week 12:** The participants will continue study treatment at the same dose up to Week 16.

**After Week 16:** Study treatment will continue as long as it remains beneficial for the participant, but up to a maximum of 5 years after last participant first visit [see Section 3.1.2 for details].

**EOT visit:** This visit should be conducted within 1 week of the last dose of study treatment.

[figure not shown]
**Safety Follow-up period:** Starts on the day after the last dose of study treatment and ends about 30 days thereafter with a phone call that will serve as the End-of-Study (EOS).

The visit schedule and protocol-mandated procedures will be performed according to the table of assessments [Table 4, Table 5] and are described in Section 7.

The overall study design is depicted in Figure 2.

Confidential

Figure 2 Study design

b.i.d twice daily; D day; eq. equivalent; EOS End of Study; EOT End of Treatment; FU follow up;  
 M month; q every; V visit; W week.  
 Equivalent (eq.) refers to the equivalent dose according to the body weight category as described in Section 5.1.4.

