### 6.2 Safety endpoints

- Treatment-emergent AEs (TEAEs) occurring up to EOT + 3 days.
- Treatment-emergent SAEs (TESAEs) occurring up to EOT + 3 days.
- AEs leading to permanent discontinuation of study drug.
- Treatment-emergent deaths (all causes) occurring up to EOT + 3 days.
- Treatment-emergent marked laboratory abnormalities (hematology and blood chemistry tests) over time occurring up to EOT + 3 days.
- Change from baseline in selected hematology and blood chemistry laboratory variables over time up to EOT + 3 days.
- Treatment-emergent ECG abnormalities over time occurring up to EOT + 3 days.
- Change from baseline in TSH over time up to EOT + 3 days.
- Change from baseline in vital signs (blood pressure, heart rate) over time up to EOT + 3 days.
- Change from baseline in height and body mass index over time up to EOT + 3 days.
- Change from baseline in sexual maturation (Tanner stage) over time up to EOT + 3 days.

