**Table 4 Visit and assessment schedule until Week 16**

Period	Screening	Base-line/ Enrollment	Treatment													
			Up-titration												Maintenance	
Name	Screening visit / Visit 1	Visit 2	Visit 3 b or Tel	Visit 4	Tel. a W3	Visit 5	Tel. a W5	Visit 6	Tel. a W7	Tel. a W8	Tel. a W9	Tel. a W10	Tel. a W11	Visit 7	Tel. a W14	Visit 8
Time	≤ 42 days before Day 1	Day 1	Week 1 Day 5 1 / +2 d	Week 2 Day 15 ± 3 d	Week 3 Day 22 ± 3 d	Week 4 ± 3 d	Week 5 ± 3 d	Week 6 ± 3 d	Week 7 ± 3 d	Week 8 ± 3 d	Week 9 ± 3 d	Week 10 ± 3 d	Week 11 ± 3 d	Week 12 ± 3 d	Week 14 ± 3 d	Week 16 / M4 ± 3 d
Written informed consent	X															
Inclusion/exclusion criteria (incl. hemodynamics)	X															
Med. History incl. PAH diagnosis	X															
Previous/Concomitant medications	X	X				X		X						X		X
Mod. NYHA/WHO FC	X	X														X
Panama FC	X	X														X
PAH signs/symptoms	X	X														X
PAH-related non-pharmacological interventions			If applicable													
Physical examination	X l	X k				X k								X k		X k
Growth: Weight and height	X m	X												X		X m
Vital signs (blood pressure, heart rate)	X	X				X								X		X
ECG		X	X g			X								X g		X
Echo n		X														X
6MWD test h		X i														X

Pulmonary arterial hypertension

Protocol AC-065A203

Confidential

Amendment 7 Version 8

30 September 2021, page 81/154

Period	Screening	Base-line/ Enrollment	Treatment													
			Up-titration												Maintenance	
Name	Screening visit / Visit 1	Visit 2	Visit 3 b or Tel	Visit 4	Tel. a W3	Visit 5	Tel. a W5	Visit 6	Tel. a W7	Tel. a W8	Tel. a W9	Tel. a W10	Tel. a W11	Visit 7	Tel. a W14	Visit 8
Time	≤ 42 days before Day 1	Day 1	Week 1 Day 5 1 / + 2 d	Week 2 Day 15 ± 3 d	Week 3 Day 22 ± 3 d	Week 4 ± 3 d	Week 5 ± 3 d	Week 6 ± 3 d	Week 7 ± 3 d	Week 8 ± 3 d	Week 9 ± 3 d	Week 10 ± 3 d	Week 11 ± 3 d	Week 12 ± 3 d	Week 14 ± 3 d	Week 16 / M4 ± 3 d
Tanner stage	X															X
Childbearing potential	X	X	X	X		X		X			X			X		X
Pregnancy test (if appl.) e	X	X				X				X				X		X
Laboratory test, Hematology/Chemistry f	X	X				X								X		X
TSH		X				X								X		X

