  - k. Physical exam only for areas of interest (general appearance, cardiovascular, and respiratory system).
  - l. Complete examination.
  - m. Height required at Screening and Week 16 only.
  - n. Echocardiography should be performed prior to physical exertion (eg, 6MWT).
- 6MWD 6 minute walk distance; 6MWT 6 minute walk test; d day(s); appl. applicable; ECG electrocardiogram; h hour(s); iMTD individual maximum tolerated dose; M month; Mod. modified; NT pro BNP N terminal pro b type natriuretic peptide; NYHA New York Heart Association; PK pharmacokinetic(s); Tel. telephone call; TSH thyroid stimulating hormone; W week; WHO FC World Health Organization functional class.

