#### **7.2.3.4 Weight and height**

Height will be measured using a stadiometer at Screening and at Week 16, every 3 months for 1 year following Week 16, then every 6 months. Body weight will be measured in indoor clothing but without shoes.

Confidential

Body weight and height are measured and recorded in the eCRF.

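### Week 12 BMI is computed with the Screening height, so its change from baseline repeats the weight change, ignores growth, and is followed by an artificial step down at Week 16

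*SAP*

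**What the plan says.** SAP section 4.6 (Body Weight and Height) sets the BMI rule by period. For the early visits: "Before Week 16, BMI is calculated by using height from screening". At Week 16 the Week 16 height is used, and then: "After Week 16, BMI will be calculated from the height and weight collected at each visit". The planned output is: "Values and changes from baseline over time for weight, height and BMI will be summarized by age cohort and body weight group". Growth curves for height, weight and BMI are also planned. No caveat on the age of the height is given.

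The rule follows the protocol's data collection. In Table 4 the row "Growth: Weight and height" is marked at Screening, Baseline, Week 12 and Week 16, but footnote m restricts it: "Height required at Screening and Week 16 only". Protocol 7.2.3.4 agrees: "Height will be measured using a stadiometer at Screening and at Week 16, every 3 months for 1 year following Week 16". Table 5 marks weight and height at the EOT visit.

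The variable affected is a listed safety endpoint in Protocol 6.2: "Change from baseline in height and body mass index over time up to EOT + 3 days".

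**The concern.** These are children aged 2 to under 18, many of them still growing. A current weight divided by the square of an old height gives a BMI that is too high. The affected quantity is a named safety endpoint. Protocol 1.4.2 lists monitoring of growth among the measures to limit risk, and Protocol 1.2.3.4.2 reports decreased weight as a common adverse event in adults. A rule that hides part of an early BMI decline therefore errs in the unfavourable direction. When the measured Week 16 height enters, the growth accumulated since Screening is applied in one step, which looks like a sudden loss.

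**Working it through.** The documents state no figure on this point, so there is none to reproduce.

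**Inputs from the documents**
- Scheduled weights up to Week 16: Screening, Baseline, Week 12, Week 16 (Protocol Table 4).
- Scheduled heights in the same period: Screening and Week 16 only (Table 4 footnote m; Protocol 7.2.3.4).
- Screening: "Lasts up to 42 days; starts with the signature of the informed consent form" (Protocol 3.1.1). The height used at Week 12 is thus 12 to 18 weeks old, give or take the 3-day visit window.

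**Assumed inputs (not in the documents):** growth 5-8 cm/year, height 85-115 cm, BMI 15 kg/m2.

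**Change at Week 12.** Let hs be the Screening height, and W0 and W12 the weights. Computed BMI is W0/hs² at Baseline and W12/hs² at Week 12. Their ratio is W12/W0, because hs cancels. The percent change in BMI is exactly the percent change in weight.

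**Size.** Computed BMI divided by true BMI is (true height / Screening height)². With growth rate g, height age w weeks and Screening height h, the error is ((h + g·w/52)/h)² − 1.

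| | 5 cm/year, 115 cm | 8 cm/year, 85 cm |
|---|---|---|
| Week 12, no screening gap (w = 12) | (116.15/115)² − 1 = 2.0% | (86.85/85)² − 1 = 4.4% |
| Baseline, 6-week gap (w = 6) | (115.58/115)² − 1 = 1.0% | (85.92/85)² − 1 = 2.2% |
| Week 12, 6-week gap (w = 18) | (116.73/115)² − 1 = 3.0% | (87.77/85)² − 1 = 6.6% |
| Error in change at Week 12, 6-week gap | 3.0 − 1.0 = 2.0% | 6.6 − 2.2 = 4.4% |

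The error in change from baseline is thus about 2.0-4.4% whatever the screening gap. At a BMI of 15 that is 0.020 × 15 = 0.30 to 0.044 × 15 = 0.66 kg/m2. It is zero when growth is zero.

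**Week 16.** The BMI value is correct. Its change from baseline is biased only through the baseline height: zero with no gap, and down by 1.0-2.2% with a 6-week gap. The drop between the Week 12 and Week 16 points that is due to the rule alone equals the error in the Week 12 value: 2.0-4.4% with no gap, 3.0-6.6% with a 6-week gap.

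**What is masked.** Take a child of 125 cm and 25.8 kg growing 6 cm/year with no weight change and no screening gap. True BMI falls by 0.36 kg/m2 by Week 12 and by 0.48 by Week 16. The SAP rule reports 0 at Week 12 and −0.48 at Week 16, so a gradual decline appears as a sudden one.

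**Early EOT.** Height is scheduled at EOT. Read literally, the rule for visits before Week 16 would still apply the Screening height to an EOT in that period and set aside a height measured the same day.

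**The case against.** The best defence is that this is an openly stated convention forced by the protocol's height schedule. Weight and height are each summarised and plotted separately, all safety analyses are descriptive, the primary objective is pharmacokinetic, and no BMI threshold or dose decision uses the Week 12 value. All of this stands and keeps the point minor. It does not justify the rule, because omitting the Week 12 BMI, or interpolating height for it, needs no new data.

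The SAP's phrase on the time points for BMI could also be read as covering only Screening and Week 16. The separate rule for visits before Week 16 makes that reading unlikely.

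A reader might infer more than the documents support:
- **That weight loss is hidden at Week 12.** It is not. Baseline and Week 12 share one height, so a 5% weight loss appears as a 5% BMI fall.
- **That the endpoint is wrong by up to 6.6% (about 1.0 kg/m2 at a BMI of 15).** That is the error in the Week 12 value. The endpoint is change from baseline, where growth during the screening gap cancels.
- **That BMI is wrong throughout the first 16 weeks and shows a false loss at Week 16.** Only one scheduled post-baseline visit is affected, the Week 16 value is correct, and no Week 12 to Week 16 contrast is planned.
- **That this is mainly a problem of the youngest cohort.** At an assumed 6 cm/year, the error in change at Week 12 is about 0.43 kg/m2 at 100 cm (BMI 15.5), 0.37 at 125 cm (BMI 16.5) and 0.36 at 155 cm (BMI 20). The relative error is larger in shorter children, but the absolute sizes are similar while growth continues.

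**Conclusion.** The point holds as a minor flaw in one derived variable. Change from baseline in BMI at Week 12 contains no information beyond change in weight and is biased upward in growing children, by about 2.0-4.4% (0.3-0.7 kg/m2 at a BMI of 15), falling to near zero when growth is complete. It masks a BMI fall due to growth without weight gain and puts an artificial step between the Week 12 and Week 16 points in tables and curves. From Week 16 on, BMI values are correct, and change from baseline carries only a small downward bias from a baseline height up to 42 days old. The existence and direction of the error follow from the documents. The size rests on the assumed growth rates, heights and BMI.

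**What to change.** Amend the derivation in SAP 4.6:
1. Derive BMI from same-visit height wherever height is measured, including any EOT before Week 16.
2. Keep baseline BMI on pre-dose measurements only. Interpolating the baseline height towards Week 16 would make baseline depend on an on-treatment measurement, against the definition in SAP 2.4.
3. At Week 12, show weight only. Alternatively, use a height interpolated linearly between Screening and the next measured height, and show weight only where no later height exists.

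This needs one changed derivation rule and no new visits or data. The downside is that Week 12 BMI is either dropped or model-derived. If it is interpolated, its change from baseline keeps the same small downward bias as at Week 16.

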### 1.4.2 Risks

The tolerability and safety profile of selexipag administered to children is expected to be consistent with that of adult patients [see Section [1.2.3.4](#)].

The following measures are being taken to minimize the potential risks for the pediatric participants participating in the study:

- The selection of the starting dose for pediatric participants is based on their body weight category, using the data from the population PK model in the GRIPHON study, targeting the exposure observed in adult participants with PAH at a starting dose of 200 µg.
- At the interim and final PK analyses, all available PK results will be used to update the PK model and to confirm or adjust the dose selection.
- Enrollment of Cohort 3 (children aged from 2 to less than 6 years old) will only be performed after the PK interim analysis in Cohorts 1 and 2 (pediatric participants older than 6 years) have been completed, and selexipag safety and tolerability profiles in Cohorts 1 and 2 have been confirmed.
- The number of PK samples and blood volume collected per participant will be optimized to reduce the total amount of blood drawn from pediatric participants [see Section 7.2.5.1].
- Inclusion and exclusion criteria are carefully designed in this protocol [see Section 4].
- Close monitoring during the initial up-titration period up to Week 12 includes weekly phone calls or site visits, followed by 3-monthly contacts (phone calls and site visits alternating every 3 months) [see Figure 2, Table 4, and Table 5].
- Specific recommendations are made regarding the management of AEs associated with tolerability during the initial up-titration phase [see Section 5.1.4], along with the recommendation that participants take study drug with food to improve tolerability [see Section 5.1.4].
- Specific recommendations are made for study drug interruption and/or permanent discontinuation [see Section 5.1.10].
- Guidance to investigator and parents/participants in case of clinical signs compatible with gastrointestinal ileus or obstruction [see Sections 1.2.2 and 5.1.10].
- Guidance to investigator and parents/participants in case of clinical signs of hyperthyroidism [see Sections 1.2.3.4 and 5.1.10].
- Monitoring of participants' growth and development throughout their study participation [see Sections 7.2.3.4. and 7.2.3.5].

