#### **10.3.5.6 Height and Weight**

Absolute values and changes from baseline will be summarized over time up to EOT + 3 days, using descriptive statistics for continuous variables.

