4. SAFETY ANALYSIS

Safety and tolerability will be assessed throughout the study, from signing of the Informed Consent Form (ICF) until the participant's last study-related activity. The study will include the following evaluations of safety and tolerability: adverse events, clinical laboratory tests (including TSH, thyroid antibodies, T3, T4, pregnancy tests, Plasma NT pro-BNP), ECG, vital signs, growth (weight, height and BMI), sexual maturation (Tanner Stage), childbearing potential and physical examinations.

Unless otherwise specified, all safety analyses will be carried out descriptively (using the Safety Analysis Set) in the overall population, by age cohort and body weight group.

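### Height, weight and BMI are planned only as raw values and changes, with no named age- and sex-specific growth reference, so a modest slowing of growth has nothing to be compared with

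*SAP*

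**What the plan says.** Protocol 6.2 lists as a safety endpoint "Change from baseline in height and body mass index over time up to EOT + 3 days". Protocol 1.4.2 counts monitoring of "growth and development throughout their study participation" among the measures that limit risk to the children.

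The planned analysis is on the raw scale. Protocol 10.3.5.6, for height and weight, says "Absolute values and changes from baseline will be summarized over time up to EOT + 3 days, using descriptive statistics for continuous variables". SAP 4.6 covers weight, height and BMI: "Values and changes from baseline over time for weight, height and BMI will be summarized by age cohort and body weight group". SAP 4 sets the general layout for safety tables: "in the overall population, by age cohort and body weight group". Sex is not a stratum. SAP 7 limits continuous summaries to basic location and spread statistics. SAP 4.6 adds individual listings and states that "the growth curves will be presented for height, weight, and BMI as well".

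On timing, footnote m to Protocol Table 4 says "Height required at Screening and Week 16 only", for the period up to Week 16. SAP 2.4 takes as baseline the last value before the first dose, so baseline height is normally the screening height. SAP 4.6 then specifies "Before Week 16, BMI is calculated by using height from screening"; from Week 16 on, BMI uses the height from the same visit.

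**The concern.** A healthy child's height and weight rise with age, at a rate that depends on age and sex. A mean raw change is therefore expected growth plus or minus any effect of drug or disease. With no control arm, the expected part has to come from outside the trial, and the plan names no source for it. Age cohorts spanning 4 to 6 years with both sexes pooled do not supply one; weight groups can mix ages further. Treatment may continue until 5 years after the last participant's first visit, so long-term growth is something this study could describe.

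At stake is the interpretation of one named paediatric safety endpoint. A modest slowing would be reported as a positive mean change with no benchmark. The BMI rule is a smaller, separate matter: dividing a current weight by the square of an old height makes a growing child's BMI look too high until Week 16, when it drops back.

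**Working it through.** **1. Search of the text.** The plan states no expected growth, growth velocity or detectable deficit, so it has no figure to reproduce. In the endpoint lists, the visit schedules, Protocol 7.2.3.4, 9.5 and 10.3.5.6, and SAP 3.1, 4, 4.2, 4.6 and 7, no growth reference, z-score, centile or expected velocity is attached to measured height, weight or BMI. Centiles appear only in the Panama class descriptors (Protocol Appendix 2), an investigator-rated functional scale. By contrast, SAP 4.2 normalises certain laboratory values for age and gender.

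**2. Raw height change (illustration).** Assumptions: velocity v = 7 cm/year for a growing child, and a deficit of 1 cm/year on treatment. From the documents: a month is 28 days (Table 5), so Month 13 = 364 days; screening is up to 42 days before Day 1.

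- Change from screening height without deficit = v × (lag + 364)/365.25: 6.98 cm at lag 0 and 7.78 cm at lag 42.
- With deficit = v × lag/365.25 + (v − 1) × 364/365.25: 5.98 cm at lag 0 and 6.78 cm at lag 42.

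Pre-treatment growth in a 42-day lag is 7 × 42/365.25 = 0.81 cm (0.57 cm at v = 5, 1.03 cm at v = 9). It enters the raw change and is close to the one-year deficit of 1.00 cm.

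**3. The same deficit on a z-score scale.** Assumptions: reference height SD 5 to 7 cm; SD of change in z 0.3 to 0.5, held constant; no dropout. Mean change in z = −(days/365.25)/SD.

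| Time | Years | Mean change in z |
|---|---|---|
| Week 16 (112 d) | 0.307 | −0.04 to −0.06 |
| Month 13 (364 d) | 0.997 | −0.14 to −0.20 |
| Month 28 (784 d) | 2.146 | −0.31 to −0.43 |

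The 95% CI half-width is t(0.975, n − 1) × SD/√n: 0.17 to 0.28 for n = 15, 0.14 to 0.23 for n = 20 and 0.09 to 0.15 for n = 45. Week 16 is out of reach. One cohort at Month 13 is borderline at best.

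Pooling helps less than it appears to, because Cohort 1 (12 to under 18 years) includes adolescents at or near final height. If a third of 45 children could show no deficit, the Month 13 mean shift would fall to two thirds: 0.142 × 2/3 = 0.09 to 0.199 × 2/3 = 0.13, about the size of the half-width.

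**4. BMI before Week 16.** Screening height is up to 42 days old at Day 1 and up to 42 + 84 + 3 = 129 days old at Week 12, counting the 3-day visit window. Overstatement = ((h + g × d/365.25)/h)² − 1, with height h (cm) and velocity g (cm/year) assumed.

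| Case | Day 1 | Week 12 |
|---|---|---|
| h = 90, g = 9, longest lag | 2.31% | 7.19% |
| h = 160, g = 5, longest lag | 0.72% | 2.22% |
| h = 105, g = 7, d = 21 and 105 | 0.77% | 3.87% |

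In the mid case, with a constant true BMI of 16 kg/m², the table would show a change of +0.50 at Week 12 and −0.12 at Week 16, an artificial drop of 0.62 kg/m² between the two visits.

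**The case against.** The SAP implements the endpoint as the protocol defines it and adds weight, listings and curves; nothing contradicts. All safety analyses are descriptive. Protocol 9.5 puts growth under continuous sponsor review, with an IDMC monitoring safety data, and the Panama class, rated repeatedly up to age 16, asks whether a child keeps to their own centiles. SAP 2.3 leaves output details to a Data Presentation Plan that is not among the documents reviewed, and the growth curves could be drawn over reference centiles there. Z-scores can also be derived later from the listings. All of this stands, and it limits the point to modest slowing and to what the SAP itself specifies.

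Three stronger readings are tempting and are not supported. A reader might infer that growth harm would go unseen; marked arrest or weight loss would show in the listings, the curves and the ongoing review. A reader might infer that z-scores would reveal a drug effect with good power. The protocol itself links PAH to failure to thrive and compromised growth, so a decline could be disease, and applying one growth velocity across ages 2 to under 18 overstates what adolescents can show. A reader might also infer a serious pre-specification failure. The study is open-label and data had been extracted before the first SAP was approved, so naming a reference now is tidier but restores little.

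On BMI, the rule is openly stated, and the 7% figure combines the longest lag with a small, fast-growing child. A height taken before dosing on Day 1 would become the baseline height, although the schedule does not require one. The direction of the error in a growing child is not in dispute.

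**Conclusion.** The point holds as a gap in the analysis specification: raw summaries only, pooled over sex and wide age bands, with no named reference for tables or curves in a single-arm, multi-year paediatric study. A named reference would supply a general-population expectation of zero for the mean change in z-score, and scoring at exact age would allow for the screening lag.

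No general power claim is warranted. The gain is small at Week 16, often inconclusive for one cohort at one year, and lies mainly in longer-term pooled data from children still growing. The sizes rest on assumed velocity, deficit, reference SD and SD of change; a widening SD or dropout would reduce precision. The BMI overstatement at Week 12 is about 4% in a mid case and 2 to 7% at the longest lag, also under assumed heights and velocities.

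Priority is low to moderate. The primary PK objective is unaffected.

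**What to change.** In SAP 4.6:

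- Add height-, weight- and BMI-for-age z-scores by sex and exact age on the measurement date, from one named reference and within its age range.
- Summarise change from baseline in z-score with a 95% CI, by age cohort and pooled, beside the raw values.
- Overlay the same reference on the growth curves. If the Data Presentation Plan already names one, cite it in the SAP.
- State that the analysis is descriptive, that PAH may itself lower z-scores so a decline cannot be attributed to the drug, that fit is poorer in subgroups such as children with Down syndrome, and that adolescents near final height add little on height.
- Compute baseline BMI from screening weight and height taken at the same visit, as a stated exception to SAP 2.4, and omit or flag Week 12 BMI.

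The cost is programming; age, sex, height and weight are already collected. The downsides are imperfect reference fit in some subgroups, a baseline BMI up to 42 days before first dose and on a different date from baseline weight, and a lost or flagged Week 12 BMI. The Week 16 report would gain little.
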